	Protocol non-compliance and deviations	.34

	Serious breaches of GCP or protocol
	Update to SAE reporting with Protocol Version 1.2
13.	Ethics, Oversight and Approvals3
D	eclaration of Helsinki3
IC	CH Guidelines for Good Clinical Practice3
S	ubmissions to HRA, REC and local R&D3
Ρ	articipant Confidentiality3
Ir	vestigator Responsibility3
N	1onitoring3
Р	ublication Policy3
14.	Finances and Indemnity3
15.	Role of QIAGEN3
16.	Laboratory analysis plan3
17.	Other personnel and sponsor3
18.	References3

1. Synopsis

Trial site

Southampton General Hospital, University Hospital Southampton NHS Foundation Trust, [name], UK.

Trial locations

Emergency department (ED), Acute Medical Unit (AMU), Respiratory High Dependency Unit (RHDU), General Intensive Care Unit (GICU), medical wards and other locations, within University Hospital Southampton NHS Foundation Trust (UHS).

Aim

To evaluate the clinical impact and real-world diagnostic accuracy of routine molecular point-of-care testing for respiratory viruses including SARS-CoV-2 (the cause of COVID-19) in adults presenting to hospital with suspected COVID-19 and/or acute respiratory illness (ARI).

Design

Non-randomised, interventional, controlled study.

Population

Adults aged 18 years old and over presenting to hospital with suspected COVID-19 and/or ARI.

Sample Size

1000 participants (500 participants in the intervention group and 500 in the control group).

Intervention

Combined nose and throat swab (and lower respiratory tract samples where available) tested by QIAGEN QIAstat-Dx Respiratory SARS-CoV-2 Panel at the point-of-care with results communicated to clinical and infection control teams in real time.

Control

Routine clinical care with testing for SARS-CoV-2 by laboratory RT-PCR performed in regional Public Health England (PHE) laboratory contemporaneously, in patients not included in the intervention.

Key Assessment

Evaluation of clinical outcome measures, implementation feasibility, and real-world diagnostic accuracy.

Timing

12 months: March 2020 to April 2021 (with up to 6 months for patient recruitment)

Plus a further five years after patient recruitment has ended for data and laboratory analysis of specimens

2. Overview

Background

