Table 1. Optional additional tests for those testing positive for SARS-CoV-2 or any endemic coronavirus

Inclusion / exclusion criteria

Inclusion criteria:

- Is a patient in ED, AMU, HDU, GICU, medical wards, or another location within Southampton General Hospital, University Hospital Southampton NHS Foundation Trust (UHS)

- Aged ≥18 years old

- Can be recruited to the study within 24 hours of presentation to hospital

Plus:

- Has acute respiratory illness (ARI)*

OR

- Does not have ARI but is a suspected case of COVID-19 according to the current PHE case definition OR

- Does not have ARI or fulfil the PHE case definition of a suspected case but testing for SARS-CoV-2 is considered necessary by the responsible clinical team

*An episode of acute respiratory illness is defined as an acute upper or lower respiratory illness (including rhinitis, rhino-sinusitis, pharyngitis, pneumonia, bronchitis and influenza-like illness) or an acute exacerbation of a chronic respiratory illness (including exacerbation of COPD, asthma or bronchiectasis). For the study, acute respiratory illness as a provisional, working, differential or confirmed diagnosis must be made by a treating clinician.

Exclusion criteria:

- Not fulfilling all the inclusion criteria

- Declines nasal / pharyngeal swabbing

- Consent declined or consultee consent declined
- Already recruited to the study in the last 14 days

Further inclusion / exclusion notes

Concurrent, prior, or subsequent enrolment in another study is not necessarily an exclusion criterion; this is at the discretion of the chief investigator and will be assessed on a case-by-case basis. Local R&D measures including a "12 week exemption form" must be in place and agreed with the chief investigator that may facilitate co-enrolment in other studies.

The inclusion of pregnant women is permitted in the study. No additional risk is perceived to pregnant women or their offspring by any of the study procedures. No additional data collection or monitoring is therefore anticipated in this group. It may be especially important to include pregnant women in COVID-19 research, as infection with influenza is associated with worse outcomes in pregnancy [11]. Data on abnormalities at birth or congenital defects and other serious adverse events are collected and may be reportable (see relevant section on Safety).

Staff testing

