Non-hospitalised hospital staff members may be included in the intervention phase of the study, if they satisfy the other inclusion & exclusion criteria. The same consent and study procedure processes are followed. However, their results will not be included in analyses of most outcome measures, with the exception of time to result. Days away from work may be used as an additional outcome measure.

Participant Withdrawal

A participant, or their consultee where a participant lacks capacity, may decide to withdraw from the study at any time, without giving reason, and with no detriment to their medical care or legal rights.

The chief investigator may withdraw a patient from the study in the interests of participant safety or the integrity of the research study, or on the advice of the sponsor's representative (R&D department).

Any patient, or their consultee where a patient lacks capacity, who is withdrawing from the study has the options withdraw and have data and/or samples collected so far retained, or withdraw and have their data and/or samples destroyed (but signed consultee declaration forms, minimal personal identifiable information to record the withdrawal, and any completed point-of-care test result will be retained). Although the study procedures are very brief, if a patient loses capacity after enrolment but before the study procedures are completed, consultee consent must be sought to continue with any study procedures, or the participant must be withdrawn.

A note to file would normally be sufficient to record any withdrawal.

7. Outcomes

Primary outcome

• The primary outcome measure is the time from COVID-19 test being requested to the result being available to clinical teams.

Secondary Outcomes

- The time from presentation to hospital to COVID-19 test result
- Time spent in COVID-19 assessment cohort area
- Time to definitive ward move
- Number of bed moves •
- Duration of hospitalisation •
- Number and proportion of clinically unsuspected COVID-19 positive patients detected •
- Proportion of patients treated with antibiotics
- Proportion of patients treated with single doses or brief courses (<48 hours) of antibiotics •
- Duration of antibiotic use, days
- Proportion of all influenza antiviral use occurring in influenza positive patients •
- Proportion of all influenza antiviral use occurring in influenza negative patients •
- Time from admission to influenza antiviral commencement

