- Duration of influenza antiviral use, days and doses •
- Proportion of patients with ICU or RHDU admission •
- Proportion readmitted to hospital within 30 days •
- In hospital, 30 and 60 day mortality •
- Reliability (proportion of run failures), ease-of-use scores [12], and implementation feasibility • assessment (narrative) of QIAstat-Dx Respiratory SARS-CoV-2 Panel, used at the point-of-care.

Sensitivity, specificity, positive predicted value, negative predictive value, percentage positive agreement, percentage negative agreement, percentage overall agreement, and overall diagnostic accuracy of QIAstat-Dx SARS-CoV-2 assay (as part of QIAstat-Dx Respiratory SARS-CoV-2 Panel) compared to laboratory PCR using the PHE RdRP assay.

All outcomes are measured for the duration of hospitalisation or up to 30 days (whichever is shortest) unless specified otherwise and include medication (antibiotics and antivirals) that patients are discharged home with.

Exploratory Outcomes

Changes in viral load over time (kinetics) in upper and lower respiratory tract samples for COVID-19 positive patients.

Antibody levels and changes over time (kinetics) in blood for COVID-19 positive patients and patients positive for other 'seasonal' non COVID-19 coronaviruses.

Presence or absence of MxA at presentation in fingerpick whole blood (as tested by FebriDx) in patients with and without COVID-19.

Host response (transcriptomic) at presentation and over time in patients with and without COVID-19. Time to administration of experimental antiviral (if and when available)

8. Sample size

Proposed sample size

The sample size of 500 patient-participants is chosen pragmatically based on the current availability of the QIAstat-Dx Respiratory SARS-CoV-2 Panel test kits. The manufacturer has agreed for us to purchase this number. The kits are in high demand given the epidemic situation with limited supply.

500 patients would give a clinically meaningful assessment of a range of clinical outcome measures including time to results, time in COVID-19 assessment cohort areas, time to definitive ward move, and duration of hospitalisation. It will also allow a robust assessment of the reliability and ease-of-use of the platform. Aiming to recruit more than 500 patients may delay analysis and dissemination of results of this study and subsequent policy changes the study results may bring, especially in a fast-paced outbreak situation.

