Accepting that the prevalence of COVID-19 during the study is highly speculative at present, and so formal samples size calculation for diagnostic accuracy studies are not possible, testing 500 patients will allow us to make an ongoing assessment of the real-world diagnostic accuracy of the QIAstat-Dx Respiratory SARS-CoV-2assay compared to the current reference standard of laboratory PCR testing using the PHE RdRP assay.

The control group will be 500 patients for an adequate comparison.

9. Data collection

Demographic and clinical data will be collected for all patients at enrolment including: age, sex, ethnicity, smoking status, vaccination status, co-morbidities, medication use, symptoms, duration of illness prior to hospitalisation, observations (pulse rate, respiratory rate, blood pressure, oxygenation status), laboratory results, radiology results, antimicrobial and antiviral use prior to hospitalisation and provisional diagnosis. Data will be recorded on a Case Report Form, which we intend to be electronic (ALEA). Once patients have been discharged or after 30 days (whichever is soonest), clinical data will be collected retrospectively from electronic and physical case notes including: use of antivirals, duration of antivirals, time from assessment to antiviral use, use of side room facilities, time from assessment to isolation facility use, time to clinical stability, duration of supplementary oxygen use, duration of hospitalisation, complications including ICU and RHDU admission, representation and readmission to hospital within 30 days, final diagnosis and mortality. The number of diagnostic tests and procedures performed will also be recorded and data will also be collected on the turnaround time of respiratory virus test results in each group.

10. Data Management

The subjects' anonymity will be maintained. The study team will keep a log of each subject's name, hospital ID number, date of birth, and unique participant trial number. The participant details will be recorded on the secure NHS Edge system in a similar manner, including NHS number. This participant trial number is used on documents after screening to maintain confidentiality. Documents that are not anonymous (e.g. signed informed consent forms) will be maintained separately, in strict confidence.

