Only SAEs occurring within 30 days of enrolment or hospital discharge, whichever comes soonest, will be reported to the sponsor, with the exception of any congenital anomaly or birth defect. Congenital anomalies or birth defects will be actively recorded up to 30 days post enrolment but if discovered after this period will still be reported to the sponsor. The trial procedures are very brief and very low risk, and pregnancy commencing during the trial procedures or follow up period is both unlikely to occur and is not expected to be reported to the sponsor or REC. Participants in high dependency or intensive care units are at high risk of expected death, and therefore participants recruited in these locations who die will not be reported as an SAE to the sponsor, unless it is deemed related to the study by the PI.

The SAE conditions noted were prompted by previous respiratory virus molecular POCT studies including one that showed around 60 SAEs for just over 300 patients. A large proportion of the patient group had conditions making readmission likely and had a high background likelihood of mortality. Not a single SAE was in any way related to the study, but significant resources were taken up in reporting of the SAE without any benefit or impact upon safety. Similar criteria have been used in two previous POCT studies. Therefore, the caveats to SAE reporting for this trial have been developed to streamline the reporting process, promote efficiency and maximise safety.

Urgent safety measures

A sponsor or investigator may take appropriate urgent safety measures in order to protect research participants against any immediate hazard to their health or safety, without prior authorisation from a regulatory body. The REC must be notified immediately and in any event within three days, in the form of a substantial amendment, that such measures have been taken and the reasons why.

Protocol non-compliance and deviations

Events of protocol non-compliance or deviation will be considered by the Chief Investigator on a caseby-case basis. Where deemed necessary by the CI, advice from trials mangers, facilitators, or governance staff within UHS R&D, and as the sponsor, will be sought.

Serious breaches of GCP or protocol

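### Some ICU/RHDU admissions counted as outcomes precede the test, and the influenza-antiviral targeting outcomes need an influenza status that the design does not secure for controls

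*Protocol*

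**What the plan says.** **ICU/RHDU admission.** Section 7 (Secondary Outcomes) lists "Proportion of patients with ICU or RHDU admission". The general window in the same section is "All outcomes are measured for the duration of hospitalisation or up to 30 days (whichever is shortest"), unless specified otherwise, and nothing else is specified for this outcome. Section 9 collects it from case notes among "complications including ICU and RHDU admission".

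The inclusion criteria in section 6 admit anyone who "Is a patient in ED, AMU, HDU, GICU, medical wards, or another location within Southampton General Hospital", and the synopsis names RHDU and GICU as trial locations. Section 12 expects such recruitment: for high dependency and intensive care, "participants recruited in these locations who die will not be reported as an SAE to the sponsor", unless the death is judged related to the study. An intervention patient must also satisfy "Can be recruited to the study within 24 hours of presentation to hospital" and consent, or have a consultee agree. The Control group text in section 6 sets no location limit, no recruitment window and no consent step.

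**Influenza antivirals.** Section 7 lists the share of influenza antiviral use falling in influenza-positive patients and, separately, "Proportion of all influenza antiviral use occurring in influenza negative patients". Section 4 puts influenza A and B on the panel used for every intervention patient. The synopsis defines control care as "Routine clinical care with testing for SARS-CoV-2 by laboratory RT-PCR performed in regional Public Health England (PHE) laboratory contemporaneously". The control data items named in section 6 include neither an influenza result nor antiviral use, although that list is open-ended. Section 9 plans to record turnaround times for respiratory virus results in both groups.

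**The concern.** An outcome meant to show what a test changed should be able to occur only after the test. A patient who is in GICU or RHDU when tested already counts as an event, and no result can alter that. Such patients add the same fixed quantity to both arms if the location mix is equal, which shrinks a real difference. If the mix is unequal, they create a difference where there is none.

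The antiviral outcomes have a different weakness. The variable that sorts antiviral use into well and poorly targeted is produced by the intervention itself in one group and depends on a clinician's separate request in the other. The two shares are complements only if every treated patient has a known status. Where status is unknown, the control figures depend on how untested patients are handled, and the protocol gives no rule for that.

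**Working it through.** The protocol gives no event rate, power or location figures, and section 8 states that 500 per group is pragmatic. There is no planned figure to reproduce, so everything below except n = 500 per group rests on assumed inputs.

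**1. ICU/RHDU, dilution.** Let s be the share already in the units at testing and p the risk of later admission among the rest. The outcome as written has expectation s + (1 − s)p. Power uses the normal approximation to a two-sided 5% test of two proportions, with pooled variance under the null. Assume p = 15% v 10% and the same s in both groups.

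| s | Observed rates | Power as written | At risk per group, 500(1 − s) | Power, new admissions only |
|---|---|---|---|---|
| 0% | 15.0% v 10.0% | 67% | 500 | 67% |
| 5% | 19.25% v 14.5% | 52% | 475 | 64% |
| 10% | 23.5% v 19.0% | 41% | 450 | 62% |
| 20% | 32.0% v 28.0% | 28% | 400 | 57% |

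Check of the 10% row as written: difference 0.045, null standard error √(2 × 0.2125 × 0.7875/500) = 0.02587, alternative standard error 0.02583, (0.045 − 1.96 × 0.02587)/0.02583 = −0.22, and Φ(−0.22) ≈ 0.41. Restricted to the 450 at risk: difference 0.05, standard errors 0.02205 and 0.02198, (0.05 − 1.96 × 0.02205)/0.02198 = 0.31, and Φ(0.31) ≈ 0.62. Most of the loss therefore comes from counting prevalent cases, not from the smaller denominator.

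**2. ICU/RHDU, bias.** With the same p in both groups, the spurious difference is (1 − p)(s₁ − s₀).

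- Equal shares give zero.
- p = 10% with s = 10% v 5% gives 19.0% v 14.5%: 0.90 × 0.05 = 4.5 points, with about a 48% chance of p < 0.05 in an unadjusted test.
- Reversing the shares reverses the sign.
- For p from 5% to 15% and share gaps of 3 to 10 points, the spurious difference runs from 0.85 × 3 ≈ 2.6 to 0.95 × 10 = 9.5 points, in either direction.

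**3. Influenza antivirals.** Let q be the true share of antiviral use in influenza-positive patients and t the share of treated controls with an influenza result, with testing unrelated to status. If untested use stays in the denominator, the apparent share in positives is qt. The apparent share in negatives is (1 − q)t if unknowns are left unclassified, or 1 − qt if they are called negative. With q = 60%:

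| t | In positives | In negatives, unknowns unclassified | In negatives, untested called negative |
|---|---|---|---|
| 100% | 60% | 40% | 40% |
| 75% | 45% | 30% | 55% |
| 50% | 30% | 20% | 70% |
| 25% | 15% | 10% | 85% |

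Restricting to tested patients recovers 60% only if testing is unrelated to influenza status. That is doubtful when clinicians choose whom to test.

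**The case against.** On ICU/RHDU, a reader might infer that the outcome differs between the groups by design. The protocol does not support that. One counting rule covers both groups, and controls come from the same trust over the same period with no location limit, so controls already in the units count in the same way. Nor can the direction be assumed: the 24-hour limit is stated only for the intervention group, so controls might be tested later in their stay and more often in intensive care. Section 11 also plans multivariable adjustment. These points stand. They limit the bias to an unequal location mix, which is plausible because consent and the 24-hour window apply to one group only, but is not shown. They do not touch dilution, and adjustment for other covariates does not turn an event that precedes the test into one that follows it. Recording the item as a complication may signal an intention to count new events, but the outcome and its window do not say so.

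On antivirals, section 9 expects some respiratory virus results in controls, and section 11 gives influenza detection as an example of a between-group comparison. More influenza testing is also part of what a syndromic panel is meant to achieve, so a higher share of treatment in confirmed cases is partly a genuine effect. A reader might infer that the plan will count untested controls as negative; no passage says so, and the last column of the antiviral table shows only what such a rule would do. What remains is that some results are not a result for each treated control. Imputation for missing data, which section 11 would consider above 5%, is a weak answer for a status that routine care never required anyone to measure.

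It may also be said that these are details for an analysis plan. The outcomes, their window and the control group's defining test are fixed in the protocol, however, and no later analysis rule can supply influenza results that were never obtained.

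**Conclusion.** The point holds in two parts, both for secondary outcomes.

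- **ICU/RHDU admission** includes events that precede the test. The certain consequence is dilution wherever anyone is tested in those units: on the assumed 15% v 10%, power falls from 67% to 52% or 41% when 5% or 10% of each group is already there. Bias is conditional on a different location mix and has unknown sign; a 10% v 5% mix with no true effect would give 19.0% v 14.5%.
- **Influenza status** is ascertained for all intervention patients by design and is not secured for controls, so the two targeting shares are not measured alike and need not sum to one. On an assumed true share of 60%, half of treated controls tested would give an apparent 30%.

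The protocol gives no location mix, admission risk or influenza testing rate, so these sizes are illustrations. The definitions should be corrected, but the primary outcome is unaffected.

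**What to change.** **ICU/RHDU.** In both groups, define the outcome as new ICU or RHDU admission after the test request, among patients not in those units at that time. Include location at test request in the adjusted model. The section 7 primary outcome already starts at the test request, so the time origin should be available. The cost is a slightly smaller denominator, which on the figures above loses far less power than the present definition does, and the extraction of location at test request for controls, which section 6 does not name among their data items.

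**Antivirals.** In both groups, classify influenza antiviral use as influenza positive, influenza negative or not tested, and never count untested as negative. Add the proportion of all patients given an influenza antiviral as a between-group comparison that does not depend on influenza status. It measures use and not targeting, so it supplements the existing outcomes. Report the share in positives among tested patients as descriptive, with a note that control testing may be selective. The cost is extraction of influenza test and antiviral records for controls.

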Summaries of all baseline characteristics will be presented using means and standard deviations, medians and interquartile ranges, or frequencies and percentages, as appropriate. The groups will be compared using chi-square tests for equality of proportions for binary data (e.g. proportion of cases of influenza detected) and using independent-samples t-tests or non-parametric equivalent as appropriate for continuous data (e.g. duration of isolation facility use, etc.).

The primary outcome measure (median duration of isolation facility use) will be compared between the groups using the Mann-Whitney U test. Multivariate analysis will be performed to adjust for confounding variable in view of the non-randomised nature of the study.

12. Safety

Serious Adverse Events

The risks of respiratory tract sampling and additional blood tests being taken are minimal and where occurring are likely to be mild. No additional adverse events related to mPOCT for respiratory viruses including COVID-19 are anticipated. However active monitoring and reporting of severe adverse events will be undertaken. A Serious Adverse Event (SAE) is any adverse event that:

- Results in death

- Is life-threatening

- Requires hospitalisation or prolongation of existing hospitalisation

- Results in persistent or significant disability or incapacity
- Consists of a congenital anomaly or birth defect

In the event of a SAE, a study doctor will consider the likelihood of the event being related to the study based on the documented evidence from the treating clinicians. SAEs will be reported via the sponsor's standard forms and processes. SAEs will be reported within 24 hours of the study team learning of the SAE. In the event of a SAE, the PI will be involved in deciding whether this was a study-related event. In the event of a study-related SAE, the REC will be informed as per HRA regulations.

Participants already admitted to AMU, or another hospital ward including high dependency or an intensive care unit, or are in ED but with a decision already made to admit, are considered already hospitalised. However, an adverse event leading to prolongation of their existing hospitalisation will be counted as an SAE.

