Serious breaches of GCP or the protocol should be reported, by the investigators and the sponsor, within seven days to the Medicines and Healthcare products Regulatory Agency and relevant ethics committee in accordance with current regulations. A "serious breach" is a breach which is likely to effect to a significant degree the safety or physical or mental integrity of the subjects of the trial, or the scientific value of the trial.

Update to SAE reporting with Protocol Version 1.2

As of 3rd June 2020, 131 SAEs of deaths, life-threatening events, and readmissions have been reported to the sponsor with more expected to be found and therefore need reporting. All SAEs have been unrelated to the study procedures. Given the high rate of poor clinical outcomes during the COVID-19 outbreak unrelated to the study, and the high and unnecessary administrative burden without any safety benefit, SAE reporting for this trial urgently needs to be updated. Therefore, as of the date of approval of this amendment, the only SAEs to be reported to the sponsor are death during the hospital admission in which the participant was recruited (up to 30 days after admission; and not reportable if recruited in HDU/ICU setting), or congenital anomaly or birth defect occurring at any time. Other SAE categories shall not be reported to the sponsor unless they are related to the study. The publishing of safety outcome data for this trial is unchanged by this update.

13. Ethics, Oversight and Approvals

Declaration of Helsinki

The Investigators will ensure that this study is conducted according to the principles of the current revision of the Declaration of Helsinki.

ICH Guidelines for Good Clinical Practice

The Investigators will ensure that this study is conducted in full conformity with the ICH Good Clinical Practice (GCP) and local regulatory requirements.

Submissions to HRA, REC and local R&D

The protocol, informed consent forms, participant information sheet (and any other document requested) will be submitted to the Health Research Authority (HRA) for their processes including Regional Ethics Committee (REC) for written approval, and the study will not commence until all necessary HRA and REC approvals are in place. The Chief Investigator will submit and, where necessary, obtain approval from the REC for all subsequent substantial amendments to the protocol and informed consent document. Local R&D approval will be confirmed prior to study start.

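### Hospital stay is compared by t-test or rank test without separating death from discharge, so a mortality difference between the groups can bias it in either direction

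*Protocol*

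**What the plan says.** The secondary outcomes in Protocol section 7 include "Duration of hospitalisation" and time to definitive ward move. The measurement window is set once for all of them: "All outcomes are measured for the duration of hospitalisation or up to 30 days (whichever is shortest) unless specified otherwise". The same sentence adds that medication taken home is counted. Section 9 collects outcome data at discharge or at 30 days, whichever comes first, and does not name death as a separate end of the window, although mortality is recorded.

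Section 11 says groups are compared "using independent-samples t-tests or non-parametric equivalent as appropriate for continuous data", and gives a duration as its example. It adds a multivariate analysis for confounding without naming a model. Nowhere does the protocol mention time to discharge alive, competing events, or any rule for durations that end in death. In-hospital, 30-day and 60-day mortality are separate secondary outcomes.

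The primary outcome in section 7 is a process time: "The primary outcome measure is the time from COVID-19 test being requested to the result being available to clinical teams". Section 11 gives the primary label to a duration instead: "The primary outcome measure (median duration of isolation facility use) will be compared between the groups using the Mann-Whitney U test". That conflict is a separate point. It matters here only because an isolation duration is exposed to the same problem, while request-to-result time is hardly exposed at all.

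**The concern.** A t-test or rank test on observed stay treats a death on day 2 and a discharge home on day 2 as the same result. If the groups differ in mortality, the stay comparison then mixes how fast patients get home with how many die and when.

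A mortality difference is plausible here without any effect of the test. Intervention patients must be recruited within 24 hours of presentation, with consent or consultee assent. Controls are patients tested in routine care but not included, identified from records without consent. Patients in high dependency and intensive care are eligible, and section 12 describes them as at high risk of expected death. That section also reports that "131 SAEs of deaths, life-threatening events, and readmissions have been reported to the sponsor with more expected to be found". Adjusting for confounders may narrow a case-mix gap, but it does not change how a death is coded.

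At stake is the reading of a clinical outcome that section 8 names among those for which 500 patients are said to be informative. Time to definitive ward move has a related gap: a patient who dies, or goes home directly, before any such move has no value, and the protocol does not say how that patient is analysed.

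**Working it through.** The protocol gives no power, effect size or mortality rate for this outcome, so there is no stated figure to reproduce. Only the group size (500 each), the 30-day cap and the type of test come from the document. All other inputs are assumptions.

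**Assumptions.** Survivor stay lognormal, median 6 days, SD of log 0.9, identical in both groups. Time to death lognormal, SD of log 0.8, median varied. Mortality 25% control, 15% intervention. Two-sided 5% Mann-Whitney test.

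**Step 1: the quantity tested.** Let q be the chance that a survivor's stay exceeds a dying patient's time to death, and D the control-minus-intervention mortality difference. The chance that a random intervention stay exceeds a random control stay is

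P = 0.5 + D × (q − 0.5).

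Bias therefore needs both a mortality difference (D ≠ 0) and death times that differ from survivor stays (q ≠ 0.5). Its sign depends on q.

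**Step 2: q.** Ignoring the few ties at day 30, q = Φ( ln(6/d) / √(0.9² + 0.8²) ) = Φ( ln(6/d) / 1.204 ), where d is the median time to death.

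**Step 3: rejection rate.** The standard error of P under no difference is √(1001 / (12 × 500 × 500)) = 0.0183. The chance of a significant result in the direction of the bias is about Φ( |P − 0.5| / 0.0183 − 1.96 ). The simulation column uses 3,000 trials per row with the 30-day cap applied.

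| Median time to death | q | P | Significant, by formula | Simulated | Median stay, control v intervention (days) |
|---|---|---|---|---|---|
| 2 d | 0.819 | 0.532 | longer, 42% | longer, 41.6% | 4.6 v 5.2 |
| 4 d | 0.632 | 0.513 | longer, 11% | longer, 10.0% | 5.4 v 5.6 |
| 6 d | 0.500 | 0.500 | 2.5% each way | 2.4% longer, 2.5% shorter | 6.0 v 6.0 |
| 9 d | 0.368 | 0.487 | shorter, 11% | shorter, 10.7% | 6.7 v 6.4 |

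Longer and shorter refer to the intervention group. Chance alone gives 2.5% in each direction.

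**Step 4: sensitivity.**
- Equal mortality (20% v 20%) and the same death timing: D = 0, so P = 0.5. Simulated total rejection was 5% to 6% at every timing.
- A smaller gap (20% v 15%) with deaths at 4 days: P = 0.5 + 0.05 × 0.132 = 0.507, significantly longer in about 5%.
- The gap reversed (15% control, 25% intervention) with deaths at 4 days: excess deaths make the intervention stay significantly shorter in about 11%.
- Patients whose death is averted may stay longer than other survivors. With 20% v 10% mortality and survivors at a median of 5 days, deaths at 2 days and averted deaths staying 12 days give significantly longer in 80%. Deaths at 10 days and averted deaths staying 5 days give significantly shorter in 27%.

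**The case against.** **Silence is not a rule.** No sentence says that a death counts as a completed stay, and an unseen statistical analysis plan could add a death rule without contradicting the protocol. That is fair, and it limits the weight of the point. But the protocol does fix the window and the type of test, and those tests applied to the observed duration treat the two endings alike.

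**The stronger reading.** A reader might infer that a survival benefit would look like harm. The documents do not support this. The direction follows the timing of deaths, which the protocol does not give, and the table shows it vanishing and then reversing. A mortality difference is also required, and the protocol neither hypothesises nor quantifies one. The 131 serious events pool deaths with life-threatening events and readmissions, with no death count, denominator or control figure, so they do not establish a mortality rate.

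**A survival difference would not be hidden.** Mortality is a planned outcome, and a chi-square test detects 25% v 15% in about 98% of the simulated trials. This stands. It tells the reader that deaths differ, but it does not repair the stay comparison.

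**Ranking deaths worst is no clean remedy.** It gives a significant result favouring the intervention in about 78% of the simulated trials, but mostly because it detects the mortality difference. This stands too.

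**Observed time in hospital is a legitimate resource measure**, since a bed is occupied until death. True, and it should be kept under that name.

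**Other outcomes.** The point should not be stretched to drug durations, which also count take-home medication, nor to cohort-area time, readmission or brief antibiotic courses. For those the protocol mostly leaves detail unstated.

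**Conclusion.** The concern holds in a limited form. As written, the hospital-stay comparison does not distinguish death from discharge, and a mortality difference from case-mix or effect can bias it either way. Under the assumed 25% v 15% mortality, the intervention stay is wrongly significantly longer in about 42% of trials when deaths come at a median of 2 days and 11% at 4 days. There is no bias at 6 days, and it is wrongly shorter in about 11% at 9 days. Here wrongly means that survivors' stays are identical by construction. These figures rest on assumed mortality, death times and stay distributions; none is in the protocol.

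With equal mortality and the same death timing there is no bias, and the section 7 primary outcome is barely touched. This is a change that should be made to a secondary outcome and does not threaten the study's main comparison.

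**What to change.** - Define the stay outcome as time to discharge alive, censored at day 30, with in-hospital death as a competing event. Report cumulative incidence by group and a confounder-adjusted cause-specific or subdistribution hazard ratio.
- Handle time to definitive ward move in the same way, with death and direct discharge as competing events.
- Report observed bed-days separately and label them as resource use.
- Present the stay result beside the planned mortality outcome, because the cumulative incidence of discharge alive also depends on how many patients die.
- Use a worst-rank score for deaths at most as a sensitivity analysis, since it mixes mortality into stay.

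**Cost.** A few sentences in section 7 and section 11, or in the analysis plan. Duration of hospitalisation and mortality are already collected under section 9. The downside is that readers will see hazard ratios and cumulative incidence beside the familiar medians.
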